#### Methods

Study participation will not influence any element of IVF treatment and all patients will be receiving the standard of care at Boston IVF. For participants who meet eligibility criteria and provide informed verbal consent, baseline demographic data will be obtained from their medical record including for example; age, race, education level, height, weight, baseline semen analysis, testosterone level, follicle stimulating hormone (FSH) level. Demographic data on the female partner will include parameters such as: age, race, education level, height, weight, gravidity, parity, anti-mullerian hormone (AMH) level, and day 3 FSH.

Eligible participants will have the study introduced by the medical care team. Eligible participants will be given information on study details (see study details for participants) as well as an ejaculatory calendar/survey (see survey and calendar) that can be used if the participant enrolls in the study (see study timeline). The medical care team will inform eligible participants that they will receive a recruitment email from the research team at [contact] followed by a phone call from the research team to see if eligible participants are willing to participate (see recruitment email). Eligible participants who meet inclusion and exclusion criteria whom do not get information regarding the study from the medical care team will also receive a recruitment email. If so, the research member will call the eligible participant to obtain verbal consent to enroll in the study (see verbal consent). If the participant does not answer, a voicemail will be recorded followed by a second phone call the following day. The recruitment email and verbal consent will occur between the pre-IVF period and before stimulation day 4 of the IVF cycle. If a participant consents to enrollment, we will make a note in the treatment plan for their cycle. Enrolled participants will receive a phone call from a member of the research team during stimulation day 6 to 8 to randomize the participant to EA > 48 hours (routine care) or EA < 24 hours (see randomization call). If the participant does not answer, a voicemail will be recorded followed by a second phone call the following day.

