# Randomization

We will use computer-generated block randomization in REDCap to randomize participants in a 1:1 ratio to the EA period more than 48 hours (routine care) or less than 24 hours. Randomization will be stratified by whether the patients receive PGT-A. Research staff will call participants on stimulation day 6 to 8 to notify participants which treatment arm they were randomized to. The participant can withdraw from the study at any time if desired or will have an opportunity to not continue with the treatment arm they were randomized to. We anticipate that most of the crossovers will occur due to participants wishing to be in the alternate EA period or not being able to produce a sample in the window assigned.

The purpose of this study is to examine semen parameters with IVF/ICSI when male factor infertility patients abstain from ejaculation more than 48 hours (routine care) or less than 24 hours. Information from this study would allow us to provide evidence-based recommendations to future patients who need IVF/ICSI.

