### **B. Statistical Considerations**

# **Sample Size Justification**

Our sample size calculation is based on data from Boston IVF from 2013 to 2018 for patients with less

than 3 million total motile sperm post prep for IVF/ICSI patients. The mean number of total motile sperm is 38 million  $\pm$  24 which will be our control group. We hypothesize that the mean number of total motile sperm at the time of retrieval will increase to 48 million. In order to achieve 80% power to detect the specified difference using a two-sided alpha of 0.05, we will need 90 evaluable participants per arm. We anticipate that approximately 15% of participants will drop out or crossover, and we will inflate the sample size by another 15% to account for a non-normal distribution. Thus, we aim to randomize 117 participants per arm for a total of 234 participants.

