# **Data Analysis**

We will conduct both intention-to-treat and per-protocol analysis. Both intention-to-treat and per-protocol analyses are noted in the RCT reporting guidelines (CONSORT) as valid approaches. For this study, we will perform an intention-to-treat analysis because it is the gold standard for RCTs, even with crossover or withdraw. We also will perform a per-protocol analysis. While this analysis can introduce bias, it is a valid statistical approach.

Descriptive data will be presented as a proportion, mean with standard deviation or median with interquartile range. Comparisons will be made using Chi-square or Fisher's exact test for categorical variables and parametric or non-parametric tests for continuous variables based on data distribution. Log-binomial regression will be used to estimate risk ratios and 95% confidence intervals for the primary and secondary outcomes. While we anticipate that randomization will balance the distribution of measured and unmeasured potential confounders in the two study arms, if this is not the case, we will assess the influence of potential confounders as needed. All data will be analyzed with SAS 9.4 (SAS Institute Inc., Cary, NC, USA). All tests will be two sided and a P value <0.05 will be required to confer significance.

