# C. Subject Selection

### **Inclusion Criteria**

- Male Age 18 50 years and female age < 38 years
- First IVF cycle
- Abnormal semen parameters (at least 1 of the following on 2 semen analysis with at least one being in the past 12 months)
  - sperm concentration < 10 million/mL
  - unprocessed semen analysis with < 10 million motile sperm or processed semen analysis with < 3 million motile sperm
  - < 2 % normal forms (strict Kruger morphology)

- Female AMH > 0.7 and/or and day 2-4 FSH < 12

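### The primary analysis of total motile sperm names no baseline or PGT-A term and leaves covariates to observed imbalance; pre-specified adjustment would add precision from data already collected

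*Combined protocol and SAP*

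**What the plan says.** Under Data Analysis, continuous variables are to be compared by "parametric or non-parametric tests for continuous variables based on data distribution", which are two-group comparisons without covariates. The only model named is in the next sentence: "Log-binomial regression will be used to estimate risk ratios and 95% confidence intervals for the primary and secondary outcomes". It lists no covariate. Covariates appear once more, conditionally: the plan expects randomisation to balance confounders, and "if this is not the case, we will assess the influence of potential confounders as needed".

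Other sections show what would be available for adjustment:

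- **Methods:** the male data taken from the medical record include "baseline semen analysis, testosterone level, follicle stimulating hormone (FSH) level".
- **Inclusion Criteria:** abnormality must be shown "on 2 semen analysis with at least one being in the past 12 months". One qualifying route is "unprocessed semen analysis with < 10 million motile sperm or processed semen analysis with < 3 million motile sperm"; concentration and morphology are the others.
- **Randomization:** "Randomization will be stratified by whether the patients receive PGT-A". PGT-A is not mentioned under Data Analysis.
- **Secondary outcomes:** change from the baseline diagnostic sample is listed. This is the only analytic use of baseline semen data.

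The Sample Size Justification rests on an unadjusted comparison of means (38 against 48 million, SD 24 million) and concludes that "we will need 90 evaluable participants per arm".

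**The concern.** Two things are lost.

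**Precision.** Men differ greatly in total motile sperm: the planning SD of 24 million is 2.4 times the difference sought. If a man's earlier count predicts his retrieval-day count even moderately, putting it in the model removes part of that variation and narrows the confidence interval without enrolling anyone else.

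**A fixed primary analysis.** Under the present wording, whether to adjust, for what, and which result leads can all be decided after the arms have been compared. Randomisation already protects the type I error of a test fixed in advance; a choice between two tests made on seeing the data does not have that protection. A stratification factor that is then left out of the analysis is a further mismatch, and it also affects the pregnancy and live-birth outcomes.

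**Working it through.** **Inputs.** From the Sample Size Justification: means 38 and 48 million (difference 10), SD 24 (taken as common to both arms), two-sided alpha 0.05, 80% power, 90 evaluable and 117 randomised per arm, 15% dropout or crossover. From Randomization: 1:1 allocation. The within-arm correlation r between baseline and retrieval-day total motile sperm is not given, so r = 0 to 0.7 is an assumed range.

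**Step 1: the plan's own figure.** n per arm = 2 × [24 × (1.960 + 0.842) / 10]² = 90.4, against the stated 90. Power at 90 per arm is 79.8% by the normal approximation and 79.4% by the t-test. Also 90 × (1 + 0.15 + 0.15) = 117. The figure reproduces, and it contains no covariate term.

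**Step 2: effect of a baseline covariate.** ANCOVA multiplies the residual variance by (1 − r²). The standardised difference becomes (10/24)/√(1 − r²), and the 95% half-width at 90 per arm becomes 1.96 × 24 × √(1 − r²) × √(2/90). Power is from the noncentral t. The 99 per arm is 117 × 0.85 = 99.45, rounded down.

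| r (assumed) | Variance removed | Half-width, 90/arm (million) | Power, 90/arm | Power, 99/arm |
|---|---|---|---|---|
| 0 | 0% | 7.01 | 79.4% | 83% |
| 0.1 | 1% | 6.98 | 79.8% | 83% |
| 0.2 | 4% | 6.87 | 81.0% | 85% |
| 0.3 | 9% | 6.69 | 83.0% | 86% |
| 0.5 | 25% | 6.07 | 89.4% | 92% |
| 0.7 | 49% | 5.01 | 97.3% | 98% |

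**Step 3: log scale.** The plan expects non-normal data. For lognormal data with CV 24/38, the log SD is √ln(1 + (24/38)²) = 0.579. A ratio of 48/38 gives a standardised difference of 0.2336/0.579 = 0.403. Power at 90 per arm is then 76.7%, 77.2%, 78.4%, 80.5%, 87.4% and 96.5% for the same r values. The gain is similar to that on the raw scale.

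**Step 4: the PGT-A term.** For stratum share p and between-stratum difference D million, R² = p(1 − p)D²/24². With p of 30% to 50% (assumed), normal-approximation power at 90 per arm is 79.8% at D = 0, 80.2% to 80.3% at D = 5, and 81.3% to 81.5% at D = 10.

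**Step 5: the downside.** If baseline and PGT-A both carry no information, the standard error rises by about √(1 + 2/175) − 1 = 0.6%, and t-test power falls from 79.4% to 78.9%. In simulation (4,000 trials per r, 90 per arm, normal errors) the adjusted test's type I error was 4.6% to 5.5%, nominal within simulation error.

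**Step 6: the open choice.** As a worst case, suppose the smaller of the adjusted and unadjusted p-values is reported. In 20,000 simulated null trials per r, type I error was about 6%, 7% and 8% at r = 0.3, 0.5 and 0.7. Either test fixed in advance stayed near 5%.

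**The case against.** The unadjusted test is valid, and the trial was sized for it, so nothing in the plan depends on the missing covariates. That stands, and it is why this is an improvement and not an error.

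The gain may be small. That also stands. Eligibility selects on abnormal semen values, which can restrict the baseline range. Only one of the two prior analyses need be recent. No abstinence period is set for the baseline sample. Nothing in the documents supports r = 0.5 or 0.7 in particular.

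The adjustment is not strictly free: useless covariates would cost about half a point of power. Men may also qualify on a processed count, concentration or morphology, so an unprocessed baseline count must be confirmed as obtainable. Both points are right; both costs are minor.

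The power base can be questioned. SD 24 comes from a historical group that may differ from the men enrolled, and the 99-per-arm figures spend the extra 15% that the plan set aside for non-normality. The absolute powers are therefore conditional on the plan's own inputs. The proportional cut in variance, r², does not depend on the SD.

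The planned look at change from baseline might seem to answer the concern. It does not: it is a secondary item and leaves the primary comparison unadjusted.

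**Conclusion.** The concern holds. The primary comparison has no pre-specified baseline or PGT-A term, and the rule for admitting covariates is triggered by imbalance and left undefined. The log-binomial sentence does not fill the gap: it yields risk ratios for binary outcomes, so it cannot carry a baseline term for a continuous count.

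At 90 per arm the gain in power runs from under 2 points (r of 0.2 or less), through about 4 points (r = 0.3), to 10 points (r = 0.5) and 18 points (r = 0.7), given the plan's difference of 10 million and SD of 24 million. Almost all of it would come from the baseline count; the PGT-A term is there chiefly to match the stratified design. Even if r proves low, settling the model in advance removes a choice that could otherwise be made on seeing the results. The omission itself is certain; the size of the benefit is not. This should be changed, although the trial remains valid without it.

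**What to change.** Amend Data Analysis as follows:

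1. **Primary model.** A linear model (ANCOVA) of retrieval-day total motile sperm on arm, baseline total motile sperm and the PGT-A stratum recorded at randomisation.
2. **Baseline.** The most recent unprocessed diagnostic sample, with a rule for missing values, such as mean imputation plus a missing indicator.
3. **Scale.** Settle it before arms are compared. Either fix the log scale outright or log-transform on a stated skewness criterion applied to the pooled, arm-blind data. Put baseline on the same scale and state a rule for zeros, for example adding half the smallest non-zero value.
4. **Reporting.** The adjusted difference, or ratio of geometric means, with 95% CI. Keep the unadjusted test as a sensitivity analysis.
5. **Binary outcomes.** Include the PGT-A stratum in the pregnancy and live-birth models.
6. **Imbalance rule.** Delete it, or label it a sensitivity analysis with covariates named in advance.

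The cost is low: a short addition to the text, and a check that an unprocessed baseline total motile count can be extracted for each man. No patients, visits or tests are added.

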# C. Subject Selection

### **Inclusion Criteria**

- Male Age 18 50 years and female age < 38 years
- First IVF cycle
- Abnormal semen parameters (at least 1 of the following on 2 semen analysis with at least one being in the past 12 months)
  - sperm concentration < 10 million/mL
  - unprocessed semen analysis with < 10 million motile sperm or processed semen analysis with < 3 million motile sperm
  - < 2 % normal forms (strict Kruger morphology)

- Female AMH > 0.7 and/or and day 2-4 FSH < 12

### **Exclusion Criteria**

- Donor sperm
- Males with sperm concentration < 200,000/mL
- Utilization of a gestational carrier
- Frozen donor egg
- Female morbid obesity: BMI > 40
- History of recurrent pregnancy loss (≥2 spontaneous abortions)
- Preimplantation genetic testing (M or SR) Monogenetic disorders or chromosomal rearrangement
- The use of non-ejaculated sperm (testicular sperm extraction)

### **B4. POSSIBLE BENEFITS**

We do not know whether participants in the study will gain any direct benefit from participation. However, we hope that this study will provide data to inform how we can improve treatment for future patients with male factor infertility.

The potential benefits to the field, as a whole, are enormous. This is a clinical conundrum that is encountered daily by infertility physicians and the results of this study have the potential to change clinical practice.

### B5. POSSIBLE RISKS AND ANALYSIS OF RISK/BENEFIT RATIO

There is no clinical risk to the patient as the procedures followed are standard clinical practice.

EA > 48 hours is routine care.

The risks of EA < 24 hours:

- Lower semen volume
- Less total sperm

As there is no good evidence to guide clinical practice and these patients constitute a large volume of our practice, potential benefits far outweigh the potential risks. Given that all patients in the RCT are to be treated by ICSI, the number of sperm needed for treatment will not be compromised by EA less than 24 hours.

#### **B6. RECRUITMENT AND CONSENT PROCEDURES**

#### Recruitment

This study will utilize an opt-out recruitment method. First-time IVF/ICSI patients will be identified, and eligibility will be determined per the study inclusion and exclusion criteria prior to the start of the IVF cycle. All eligible participants will be patients of Boston IVF physicians. All Boston IVF physicians will have the option to exclude any of their patients from the study.

Eligible participants will have the study introduced by the medical care team (see script for medical care team). The medical care team will also have access to general study information (see handout for medical care team). Eligible participants will be given information on study details (see study details for participants) as well as an ejaculatory calendar/survey (see survey and calendar) that can be used if the participant enrolls in the study (see study timeline). The standard of practice for patients at Boston IVF is to receive communication via email, access many online documents, and enter the information into the online patient portal. To be consistent with this method of patient contact, participants will receive a recruitment email from the research team. The medical care team will inform eligible participants that they will receive a recruitment email from the research team at [contact] that explains the study followed by a phone call from the research team to see if eligible participants are willing to participate. Eligible participants can choose to reply back to [contact] to opt-out from receiving any more contact in regards to this study. Eligible participants who meet inclusion and exclusion criteria whom do not get information regarding the study from the medical care team will also receive a recruitment email.

#### Consent

We are requesting a HIPAA waiver for pre-screening and recruitment. For the study intervention, we are requesting a waiver of documentation of consent. Participants will be informed in the recruitment

email the study is completely voluntary. The day following the recruitment email, eligible participants will receive a phone call from a member of the research team to discuss the study and obtain verbal consent if the eligible participant is interested in participating in the study (see verbal consent). If the participant does not answer, a voicemail will be recorded followed by a second phone call the following day. The recruitment and consent process will occur between the pre-IVF period and before stimulation day 4 of the IVF cycle. If a participant consents to enrollment, we will make a note in the treatment plan for their IVF cycle. Throughout the study, we will let participants know that they have the option to stop participating at any time and that their care would not be affected by that decision.

We anticipate that a proportion of participants may desire to crossover to the other assigned EA period. If this occurs, participants will be instructed to email or call the research team. These patients would be included in the per protocol analysis. The study team will access the patients' medical records for up to 24 months following randomization in order to follow the clinical/pregnancy outcomes. These outcomes are recorded as part of routine clinical care.

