The semen sample provided on day of oocyte retrieval will be analyzed with a basic and advanced semen panel. Any remaining samples will be discarded per routine practice. Prior to providing the semen sample, participants turn in the completed survey/ejaculation history calendar to a member of the research team. Blank copies will be available for participants the day of egg retrieval if needed.

There is no clinical risk to your IVF cycle as the procedures followed are standard clinical practice. Study participation will not influence any element of the IVF treatment except for EA counseling. Currently there is no set protocol on how EA counseling is performed. Counseling on EA varies among the medical care teams at Boston IVF as some patients may or may not receive explicit EA instructions. Patients may be counseled by the medical care team with recommendations to abstain for > 48 hours at the time of their consult. All patients in this study are using ICSI to fertilize eggs and the number of sperm needed for treatment will not be compromised by ejaculatory abstinence < 24 hours. Participants who crossover to the alternate treatment arm will continue their participation in the study so that we can collect cycle outcome data. IVF stimulation protocols will be according to standard practice. ICSI and embryology practice will follow standard practice. Selection of embryos will be based on the current embryology laboratory selection protocols or by preimplantation genetic testing for aneuploidy (PGT-A). The number of embryos transferred will be based on the usual American Society of Reproductive Medicine guidelines. Any unused embryos will be disposed of or cryopreserved per

standard clinical protocols.

Outcomes

*Primary:* Total motile sperm (motility x concentration x volume)

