# **Subject Protection**

This is a completely voluntary study. Participants may withdraw from the study at any point; they also may choose to not continue with their randomized EA period. Participants will be advised that if they withdraw or choose to cross over to the other treatment arm their clinical care will not be influenced in any way.

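### The plan places crossovers in the per-protocol analysis without defining that set; this defeats the analysis's purpose and conflicts with the sample-size section

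*Combined protocol and SAP*

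**What the plan says.** Data Analysis plans both an ITT and a per-protocol analysis. Of the first it says "we will perform an intention-to-treat analysis because it is the gold standard for RCTs, even with crossover or withdraw". Of the second it says "While this analysis can introduce bias, it is a valid statistical approach". It does not state who belongs to the per-protocol set, in which arm they are counted, or what counts as adherence.

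The only membership statement is in the Consent section. After explaining that participants who want the other abstinence period should contact the research team, it adds: "These patients would be included in the per protocol analysis".

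Four other places bear on the point:

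- **Methods** keeps crossovers under follow-up: "Participants who crossover to the alternate treatment arm will continue their participation in the study so that we can collect cycle outcome data".
- **Randomization** gives the expected reasons: "most of the crossovers will occur due to participants wishing to be in the alternate EA period or not being able to produce a sample"; the last of these refers to the assigned window.
- **Subject Protection** says of participants that "they also may choose to not continue with their randomized EA period".
- **Sample Size Justification** says "we will need 90 evaluable participants per arm", followed by "We anticipate that approximately 15% of participants will drop out or crossover".

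**The concern.** A per-protocol analysis asks what happened among participants who did what they were assigned to do. Crossovers are the clearest case of those who did not, and the Consent sentence puts them in. The sample-size section treats them the other way, as part of the allowance on top of the evaluable number. Data Analysis, where the rule belongs, does not settle the matter.

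Once crossovers are in, they can be counted in only two ways. In the randomised arm, the analysis does not isolate adherers. By the abstinence actually used, it is an as-treated comparison under a per-protocol label. Crossing is then not random, because the plan expects it to follow from preference or from inability to produce a sample in time. The second reason could plausibly be related to semen output, the primary outcome.

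Two analysts following the same text could therefore report different per-protocol results from the same data. If the rule is chosen after outcomes are seen, the choice can be driven by the result.

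**Working it through.** **Inputs from Sample Size Justification.** Control mean 38 million; spread 24 million, read as a standard deviation although the text does not label it; hypothesised mean 48 million, so a difference of 10; two-sided alpha 0.05; power 80%; 90 evaluable and 117 randomised per arm; 15% for dropout or crossover combined; another 15% for non-normality.

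**The plan's own figures.** n per arm = 2 × (1.96 + 0.842)² × 24² / 10² = 90.4, or 91 when rounded up. The stated 90 gives 79.8% power. Also 90 × (1 + 0.15 + 0.15) = 117. The sample size reproduces, so this point does not rest on an error there.

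**Does the choice of rule matter?** Assume 15% cross in each arm, no dropout, and crossing unrelated to prognosis.

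- Counted as randomised: expected difference 10 × (1 − 2 × 0.15) = 7.0 million; power at 117 per arm about 61%.
- Excluded: expected difference 10 million; 117 × 0.85 = 99.45 per arm; power about 84% before any non-normality allowance.

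**Selection bias under the as-treated reading.** Assume no true effect, a share a crossing out of one arm and none out of the other, and crossovers lower by a gap g. The formula depends on how the gap is measured:

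- From the arm mean: as-treated bias = 2ag / (1 − a²); bias with crossovers excluded = ag / (1 − a).
- From the non-crossers: as-treated bias = 2ag / (1 + a); bias with crossovers excluded = ag.

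If 7.5% cross in each arm and only one arm's crossovers have the gap, the as-treated bias is 2 × 0.075 × 10 = 1.50, or 1.50 × 0.925 = 1.39 with the gap measured from non-crossers. With exclusion it is 0.75 / 0.925 = 0.81, or 0.75.

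In the table, paired values use the gap from the arm mean and from non-crossers, in that order. Bias is in millions.

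| Assumed case | As-treated bias | Bias with crossovers excluded |
|---|---|---|
| 5% cross one way, g = 10 | 1.00 / 0.95 | 0.53 / 0.50 |
| 15% cross one way, g = 5 | 1.53 / 1.30 | 0.88 / 0.75 |
| 15% cross one way, g = 10 | 3.07 / 2.61 | 1.76 / 1.50 |
| 7.5% cross each way, g = 10 in one arm only | 1.50 / 1.39 | 0.81 / 0.75 |

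The sign reverses if the gap is reversed or belongs to the other arm. With equal crossing and equal gaps the bias is zero. In the one-way cases exclusion removes a fraction (1 − a) / 2 of the bias: 47.5% at a = 0.05 and 42.5% at a = 0.15.

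With 24 million as the standard deviation, the standard error is about 3.14 to 3.17 million. The false-positive rate is then about 6% in the first row, 7 to 8% in the second and fourth, and 13 to 16% in the third.

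**The case against.** The strongest reply is that this is one loose sentence in a consent section and that the statistical section leans the conventional way. The sample-size text treats crossovers as losses, ITT is called the gold standard, and the plan already warns that per-protocol can be biased. Much of this stands. It shows that the sentence may be a slip, but nothing in the documents corrects it. A general warning about bias does not tell a reader who is in the set.

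Three stronger readings are tempting, and the documents do not support them:

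- *That the trial's main comparison is compromised.* Crossovers stay under follow-up and ITT is planned even with crossing, so the randomised comparison is untouched.
- *That the false-positive rate is 13 to 16%.* That case needs the whole combined 15% allowance to be one-way crossing, with no dropout, and a prognostic gap as large as the entire hypothesised effect. The milder cases give about 6 to 8%. None of the splits or gaps comes from the documents.
- *That counting crossovers as randomised simply repeats ITT.* This holds only if few others leave the set. Withdrawals are allowed, and abstinence of 24 to 48 hours fits neither window, so the two sets could differ.

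Nor does the sample-size allowance prove that exclusion was intended; it only fits it. An openly labelled as-treated analysis would also remove the ambiguity, and it would stay closer to the Consent wording.

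**Conclusion.** The point holds and should be fixed. The stated rule is wrong for an analysis called per-protocol, it conflicts with the sample-size section, and no definition elsewhere overrides it. The consequence is limited to the per-protocol result and to any conclusion drawn from it.

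Under the randomised-arm reading there is no added selection bias, but adherers are not isolated. Under the as-treated reading the bias is roughly 1 to 3 million against a hypothesised effect of 10 million, in either direction. That range rests on assumed gaps of 5 to 10 million, assumed crossing of up to 15%, and 24 million as the standard deviation. It illustrates the mechanism and does not predict what this trial would show. Excluding crossovers reduces the bias but leaves more than half of it in these cases, which is why the per-protocol analysis should be supportive under any rule.

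**What to change.** Reconcile the Consent, Data Analysis and Sample Size Justification sections before outcome data are seen.

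1. Replace the Consent sentence with: *Crossovers are analysed in their randomised arm in the intention-to-treat analysis and are excluded from the per-protocol analysis.*
2. In Data Analysis, name ITT as primary and per-protocol as supportive. The section favours ITT but does not formally rank the two.
3. Define the per-protocol set as participants whose recorded time from last ejaculation to the retrieval-day semen sample falls in the assigned window (<24 h or >48 h). State that reference time explicitly, because Procedure counts from the day of retrieval and the secondary outcomes refer to time to retrieval. Use the calendar/survey if it records time finely enough; the form is not in the documents, so this must be checked.
4. Report crossovers, abstinence of 24 to 48 hours and missing records by arm, with reasons.
5. If an analysis by abstinence actually used is wanted, label it as-treated and exploratory.

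**Cost.** The text change is small and the ITT sample does not change. The per-protocol set shrinks. If the full 15% is lost, 117 × 0.85 = 99.45, so about 99 per arm remain. Keeping the 15% non-normality allowance, the effective size is 99.45 / 1.15 = 86.5 per arm, with power about 78%. On the same basis, about 80% power needs 90 × 1.15 = 103.5 per arm, and the set falls below that once losses pass 1 − 103.5 / 117 = 11.5%. Losses from 24 to 48 hour abstinence and missing records may come on top, and the documents do not bound them. Blank calendars offered on retrieval day should limit the missing ones.
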